The active component of BSS with antimicrobial effects is bismuth, which is poorly absorbed and mostly remains in the GI tract while salicylate is systemically absorbed in the stomach (9). The mechanism of action of BSS in the prevention of TD is thought to be due to bismuth's intraluminal antimicrobial properties and a reduction in the number of bacteria (4, 6, 9, 10). In-vitro studies suggest that bismuth's action is bactericidal (6, 11), even at various levels of intestinal pH and against a wide range of organisms (11). The precise mechanisms of action include the binding of ingested bacteria and subsequent marking of these organisms to be killed by host defenses, rendering the bacteria unable to attach to receptor sites that are important for colonization and infection (11), degrading the bacterial cell wall, inhibiting ATP synthesis, and inhibiting the function of the plasma membrane (9). This inhibition may occur in as little as 0.5–24 hours (9). BSS may also inactivate bacterial toxins before attachment to the intestinal mucosa (12). Viruses may be inhibited by BSS; it may prevent viral invasion and deter replication through unknown mechanisms (4).

There is a current domestic and international focus on preventing the acquisition of drug-resistant enteric bacteria by high-risk groups, including travelers (13). International travelers are at increased risk for acquiring gut organisms containing AMR genes (especially after travel to Asia), developing TD, taking antibiotics, and requiring hospitalization (14, 15, 16, 17). Although carriage of organisms containing gut AMR genes may be transient in most travelers (15), it can persist for ≥1 year in over 10% of travelers, increasing the risk of transmission to household members and others (18). Avoiding the use of antibiotics while abroad is one way to lessen acquisition of antibiotic-resistant organisms (19). BSS treatment of adult outpatients with acute diarrhea has been found to reduce antimicrobial medication use in a high prevalence area (20). It is currently unknown whether BSS affects the acquisition of gut AMR genes while traveling abroad; however, given BSS' antimicrobial properties, stability in acidic conditions, and blockage of receptor sites to prevent colonization, it is possible that prophylactic BSS may indirectly prevent acquisition of AMR genes in international travelers by preventing intestinal colonization of ingested microbes. More research must be done to address this uncertainty.

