Study Design and Location(s)

This study will be conducted as a double-blinded, placebo-controlled randomized clinical trial.

We propose two arms to test BSS against placebo:

1. BSS 4 tablets po bid (2.1 grams total of BSS)
2. Placebo 4 tablets po bid

Study participants will be recruited from The New York Center for Travel and Tropical Medicine Clinic in New York, New York, USA (see Procedures) (<http://www.travelhealth.net/>). Throughout the study period, the recruiting site will maintain adequate personnel trained in the study protocol and procedures (see Training for Study Personnel). Study personnel will be available to communicate with the co-PIs as necessary and to address issues with the study protocol and concerns of the study participants. This site will be able to consent and enroll participants (see Procedures for Implementing and Documenting Informed Consent), store and distribute the study drug and placebo, and collect and safely store questionnaire data (see Data Handling and Analysis) and biologic samples (stool) data (see Biologic [stool] Specimen Collection and Testing), in accordance with the study protocol.

Objectives

1. (Hereafter, “primary objective”) Test the efficacy of BSS in the prevention of TD among international travelers.
2. (Hereafter, “secondary objective”) Determine the impact BSS has in the acquisition of gut AMR genes among international travelers.

Hypotheses

The following hypotheses follow the objectives above:

1. NULL HYPOTHESIS: BSS does not prevent TD among international travelers.
 - a. Does BSS prevent TD among international travelers?
 - b. Does BSS reduce severity/frequency of TD among international travelers?
2. NULL HYPOTHESIS: BSS does not alter the acquisition of gut AMR genes among international travelers.
 - a. Does BSS affect the acquisition of gut AMR genes among international travelers?

- b. Does BSS affect the acquisition of gut AMR genes among international travelers that develop TD?
 - i. Does BSS alter the acquisition of gut AMR genes if an international traveler with TD takes an antimicrobial while taking BSS?
- c. Does BSS affect the acquisition of gut AMR genes among international travelers that do not develop TD?

General Approach

The approach of this study will be hypothesis-testing.

Procedures and Methods

Design

Statement of Purpose

The purpose of this study is to investigate the impact of BSS on the acquisition of TD and acquisition of gut AMR genes among international travelers.

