Includes the 7 days prior to departure in which the pre-travel questionnaire and a biologic (stool) specimen is collected, the full duration of travel, and through 10 days maximum post-return from travel, or until both the post-travel questionnaire and submission of the post-travel biologic (stool) specimen is complete (a maximum of 17 days post-travel)

Travel companion (group):

Two or more study participants with a common relation (friends, colleagues, or relatives) with the same itinerary, who anticipate performing the same activities during travel

Trip duration:

The number of days spent in country; excludes air travel time

Severe TD:

Hospitalization to an inpatient ward either during travel or after travel with a diagnosis of diarrhea

Acquisition of AMR gene(s):

The presence in a post-travel biologic (stool) specimen of one or more antimicrobial resistance gene(s) that were not present in a pre-travel biologic (stool) specimen from the same person, and which is known to confer antimicrobial resistance to one or more antimicrobial agents ("resistome")

Medication compliance:

Full = participant takes all scheduled doses according to directions

Good = If <15% of BSS or placebo doses were missed during travel

Fair = If 15–30% of BSS or placebo doses were missed during travel

Poor = If >30% of doses were missed during travel

Questionnaire compliance:

Full = participant completes all questionnaires

Good = participant completes >80% of all during travel questionnaires, AND
both the pre- and post-travel questionnaires

Fair = participant completes between 30–80% of all during travel
questionnaires, including AT LEAST the pre-travel questionnaire

Poor = participant completes <40% of all during travel questionnaires, and AT
LEAST the pre-travel questionnaire

Biologic (stool) specimen compliance:

Full = BOTH specimens collected and sent

Fair = ONLY one specimen collected and sent

Poor = No specimens collected and sent

Loss to follow-up:

Failure to complete the post-travel questionnaire after three attempts to contact the participant or if submission of the post-travel biologic specimen (stool) occurs more than 10 days after return from travel or is not submitted

Participant Inclusion Criteria

Willing participants must meet the inclusion criteria as outlined here:

1. Be ≥ 18 and <70 years of age at the time of enrollment

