9. Have had diarrhea (see Definitions) anytime in the previous 30 days, have diarrhea at the pre-travel consultation, or develop diarrhea before departure
10. Have been given doxycycline for malaria prophylaxis for the current trip (due to possible drug-drug interactions and decreased absorption of the doxycycline) (27)
11. Have an allergy to any component of the placebo tablets

Estimated Number of Participants

We anticipate enrolling approximately 500 participants (see Sample Size and Power Calculation).

Sample Size and Power Calculation

A sample size of 488 participants with full compliance to medications and questionnaires (244 participants in each arm) is needed to fulfill the objectives [anticipated incidence of the endpoint as 40% incidence of TD with a 30% minimum intervention protection ($0.40-[0.4 \times 0.30] = 0.28$) with an alpha of 0.05, and 80% power].

Recruitment and Enrollment

All international travelers undergo a screening questionnaire at their pre-travel consultation to determine eligibility. This short questionnaire includes questions regarding the travelers' [see **APPENDIX A**]:

1. Age
2. Travel destination(s)
3. Trip duration
4. Acute and chronic medical conditions, including diarrhea
5. Contraindications to BSS administration
6. All current medications, including antibiotic use within the 30 days before screening
7. Willingness to participate in the trial and comply with the data collection requirements

This screening questionnaire will be administered to the traveler by study personnel at The New York Center for Travel and Tropical Medicine. The purpose will be to exclude those travelers who do not meet all inclusion criteria and those who meet any exclusion criteria (see Participant Inclusion / Exclusion Criteria). Travelers who meet the inclusion criteria and do not meet any exclusion criteria will be introduced to the project objectives and procedures, including the procedures for biologic (stool) specimen collection (see Laboratory instruments).

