Participants will be provided two OMNIgene gut kits at their pre-travel consultation/enrollment visit once enrolled (see Biologic [Stool] Specimen Data Collection and Testing). These kits will come with instructions on use, handling, and shipment.

In the event that participants are able to provide a stool sample while in clinic for their pre-travel consultation/enrollment visit or during a non-study post-travel follow-up sick visit within 10 days of return, these samples will be aliquoted by study personnel at The New York Center for Travel and Tropical Medicine in the following manner:

*First, the required quantity will be placed in the participant's OMNIgene gut kit (per manufacturer directions) to be sent to CDC's Clinical and Environmental Microbiology Branch for resistome testing. The remainder will be frozen, and sent to CDC for analysis at a later date (note: OMNIgene gut kit does not allow for culture - a see Biologic [Stool] Specimen Collection and Testing). Only those participants who happen to have a biologic (stool) specimen collection completed at the clinic will have their stool analyzed by culture; this is not a requirement for participation and no additional compensation above that previously described will be offered.

Table 3. Schedule of LABORATORY events (secondary objective)

(Events from Table 2 still apply to these participants)

	Stages		
	Pre-travel	During travel	Post-travel
Biologic (stool) sample	X		X
Laboratory testing of stool	X		X

Analytic tests

Questionnaires: Data from the questionnaires will be analyzed for statistical significance comparing intervention vs placebo groups.

Biologic (stool) specimens: A highly multiplexed PCR assay detecting over 500 different AMR genes will be used to test the DNA extracted from all biologic (stool) specimens that were placed in the OMNIgene gut kit (see Biologic (Stool) Specimen Collection and Testing). Results will be analyzed to determine if the participants acquire gut AMR genes (changes to the “resistome”) as a result of travel and whether or not that change varied with the bismuth subsalicylate treatment received. Additionally, stool bacteriologic culture will be performed on those specimens submitted in clinic.

Intervention

We propose the inclusion of two arms to test BSS against placebo:

1. BSS 4 tablets po bid (2.1 grams total)
2. Placebo 4 tablets po bid

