	Pre-travel consultation/ enrollment visit (baseline)	During travel	Post-travel	TOTAL
Recruitment materials	\$200	N/A	N/A	\$200
Printing costs (screening questionnaire, daily travel logs, labels)	\$50	\$150	N/A ^a	\$200
Participant compensation	\$100 per participant	up to \$100 per participant (\$5 per entry)	\$100 per participant	\$150,000
Advertising	\$1,500	N/A	N/A	\$1,500
IRB Costs	\$3,000	N/A	N/A	\$3,000
Prepaid envelopes for during-travel questionnaires	N/A	\$1,000 (\$2.00 stamp)	N/A	\$1,000
Shipment of study medications from CDC to clinic	\$10,000	N/A	N/A	\$10,000
Administrative Personnel Costs: Physician PI (5%) plus study coordinator (40%) Recruitment/enrollment, documentation and completion of study forms and participant and data follow up	\$110,000	N/A	N/A	\$110,000
Travel (conferences)	N/A	N/A	\$20,000	\$20,000

TOTAL				\$295,900
--------------	--	--	--	------------------

^aNot applicable

Table 5. LABORATORY events with estimated costs

	Stages			
	Pre-travel consultation/enrollment visit (baseline)	During travel	Post-travel	TOTAL
Supplies for stool sample (OMNIgene gut kit) (n=1,000 stools or 500 participants)	\$25	N/A	\$25	\$25,000
Shipping stool sample to the clinic (n=1,000 stools or 500 participants)	\$10 per sample	N/A	\$10 per sample	\$10,000
Shipping stool samples to CDC lab from clinic (n=1,000 stools or 500 participants)	\$15 per sample	N/A	\$15 per sample	\$15,000
Diagnostic testing of stool (n=500 stools or 250 participants)				
DNA extraction	\$15	N/A	\$15	\$7,500
PCR (AMR gene assay)	\$35	N/A	\$35	\$17,500
Amplicon sequencing	\$25	N/A	\$25	\$12,500
Laboratorian (ORISE)	\$28,000	N/A	N/A	\$28,000
Bioinformatics (ORISE)	\$66,000	N/A	N/A	\$66,000
TOTAL				\$181,500

Table 6. Cumulative costs of both CLINIC and LABORATORY events from Table 4 and Table 5

Cumulative totals	Total
Clinic Events	\$295,900
Laboratory Events	\$181,500
	\$477,400

References

1. Connor B. Travelers' diarrhea. In *Yellow Book* (pp. 60–64). New York, NY: Oxford University Press; 2016.
2. Brum J, Gibb R, Ramsey D, Balan G, Yacyshyn B. Meta-analyses assessment of the clinical efficacy of bismuth subsalicylate for prevention and treatment of infectious diarrhea. [not yet published]

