APPENDIX I: Data Analysis Table Shells

Table 1. Baseline Characteristics of Participants

	BSS	Placebo	P-value
Demographics			
Age			
Sex			
Race			
Ethnicity			
Medical History			
Chronic medical conditions			
Tinnitus			
Antibiotics between 30 to 90 days prior to travel			
Probiotics within 30 days			
Travel			
Duration of travel			
Primary reason for travel			
Secondary reasons for travel			
Attended provider (by type)			

Table 2. Odds ratios (OR) of TD associated with BSS among international travelers, adjusting for select factors

	Total, N	TD, %	OR (95% CI)
Tablets			
BSS			
Placebo			Ref
Age groups, years			
≥18			
Sex			
Male			
Female			Ref
Race/ethnicity			
Travel region			
Travel duration			

Table 3. The proportion of participants having resistance genes before and after travel; acquiring, losing, or maintaining genes after travel

	All participants	BSS	Placebo	P-value
Pre-travel				
Gene 1				
Gene 2				
Gene 3				
Gene 4				
...				
Post-travel				
Gene 1				
Gene 2				
Gene 3				
Gene 4				
...				
Acquisition of gene				
Gene 1				
Gene 2				
Gene 3				
Gene 4				
...				
Loss of gene				
Gene 1				
Gene 2				
Gene 3				
Gene 4				
...				
Maintenance of gene				
Gene 1				
Gene 2				
Gene 3				
Gene 4				
...				

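### AMR acquisition is defined per participant, but the only AMR analysis shown is a gene-by-gene P-value table without error control; the number of participants tested is contradictory, and 488 carries no AMR power

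*Combined protocol and SAP*

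**What the plan says.** - **Objective.** The secondary objective is to "Determine the impact BSS has in the acquisition of gut AMR genes among international travelers". The stated rationale (Current State of Knowledge) is that BSS "may indirectly prevent acquisition of AMR genes in international travelers by preventing intestinal colonization of ingested microbes".
- **Endpoint.** Under Definitions, acquisition is the presence in the post-travel stool "of one or more antimicrobial resistance gene(s) that were not present in a pre-travel biologic (stool) specimen from the same person". This is one yes/no result per participant.
- **Analysis text.** Under Analytic tests: "Results will be analyzed to determine if the participants acquire gut AMR genes". The sentence goes on to ask whether the change differs by treatment. It names no test, effect measure or multiplicity method, and none appears elsewhere in the available text.
- **Analysis layout.** Appendix I, Table 3 is titled "The proportion of participants having resistance genes before and after travel; acquiring, losing, or maintaining genes after travel". Its rows are Gene 1, Gene 2 and so on, in five blocks (pre-travel, post-travel, acquisition, loss, maintenance), with a P-value column. No row counts participants who acquired any gene.
- **Specimens tested, methods.** Analytic tests: "A highly multiplexed PCR assay detecting over 500 different AMR genes will be used to test the DNA extracted from all biologic (stool) specimens", qualified only as those placed in the collection kit.
- **Specimens tested, budget.** Table 5 pays for kits and shipping for 1,000 stools from 500 participants, but the testing line reads "Diagnostic testing of stool (n=500 stools or 250 participants". No rule says which 250.
- **Sample size.** The Sample Size section says that 488 participants, 244 per arm, "is needed to fulfill the objectives [anticipated incidence of the endpoint as 40% incidence of TD", with 30% protection, alpha 0.05 and 80% power.

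**The concern.** The defined endpoint and the planned output do not meet. If Table 3 is completed as drawn, the report will contain many gene-level P-values and no comparison of the outcome that the plan itself defines. A reader could then pick out individual genes below 0.05, some of them there by chance, as evidence for or against the secondary objective.

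The number of participants behind the AMR result is also open. It could be everyone with paired specimens or 250 of them. If 250, they could be chosen at any time and on any basis, including after arm or illness is known.

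Finally, saying that 488 serves the objectives, in the plural, invites a null AMR result to be read as adequately powered, although no AMR quantity entered the calculation.

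**Working it through.** **1. What 488 is based on.** The inputs are all from the Sample Size section: p1 = 0.40, p2 = 0.40 × 0.70 = 0.28, alpha 0.05 (taken as two-sided), power 80%. With mean rate 0.34:

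n = [1.960 × √(2 × 0.34 × 0.66) + 0.842 × √(0.40 × 0.60 + 0.28 × 0.72)]² / 0.12² = (1.313 + 0.559)² / 0.0144 ≈ 243.4, rounded up to 244 per arm, or 488.

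The stated figure reproduces exactly from the diarrhea rates. It contains no AMR assumption.

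**2. How many stools the budget tests.** From Table 5: 500 × $15 = $7,500, 500 × $35 = $17,500 and 500 × $25 = $12,500, as printed. The column adds up: 25,000 + 10,000 + 15,000 + 7,500 + 17,500 + 12,500 + 28,000 + 66,000 = $181,500. The 250 participants are therefore built into the total and are not a slip in one cell. Testing 1,000 stools would cost 1,000 × $75 = $75,000 against 500 × $75 = $37,500, a difference of $37,500.

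**3. Chance findings in the acquisition block.** Assumptions: 500 genes tested, no true difference, each test at 0.05. The exact rejection probability at each per-gene acquisition rate (assumed) was found by enumerating both binomial arms and multiplying by 500.

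| Per-gene acquisition | Fisher, 244/arm | Chi-square, 244/arm | Fisher, 125/arm | Chi-square, 125/arm |
|---|---|---|---|---|
| 0.5% | 0.5 | 10 | <0.1 | 2 |
| 1% | 4 | 23 | 0.5 | 11 |
| 5% | 16 | 24 | 11 | 23 |
| 20% | 19 | 25 | 17 | 24 |

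The chi-square is uncorrected. The five blocks share data, so these counts should not be added across blocks.

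**4. AMR power.** The plan gives no acquisition rate or effect. For the any-new-gene endpoint with an assumed 30% relative reduction (pooled two-proportion z test, two-sided 0.05):

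| Placebo acquisition (assumed) | 244/arm | 125/arm |
|---|---|---|
| 20% | 42% | 24% |
| 40% | 80% | 52% |
| 60% | 98% | 82% |
| 80% | >99% | 98% |

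The 125 per arm assumes that the 250 split equally and all have both specimens.

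**5. Any-gene or gene count.** Simulation at 244 per arm (3,000 runs per scenario; count analyzed by negative binomial regression; all distributions assumed) shows that neither measure dominates:

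- If BSS lowers only the chance of acquiring anything (40% vs 28%), any-gene power is 79–81% and count power 36–58%.
- If BSS lowers the mean number of new genes by 30%, any-gene power is 15–88% and count power 48% to over 99%.

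**6. Sensitivity to spurious acquisitions.** If each person gains a Poisson number of spurious new genes with mean L, equal in both arms, the observed any-gene rate is 1 − (1 − p)e^(−L). At L = 1.0, 40% vs 28% becomes 1 − 0.60 × 0.368 = 77.9% vs 1 − 0.72 × 0.368 = 73.5%. Power falls from 80% to about 20% at 244 per arm, and from 52% to about 13% at 125 per arm. Spread over 500 targets, L = 1.0 is only 0.2% per target.

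**The case against.** **It is only a shell for a secondary objective.** Table 3 does not say that all 500 targets will be tested, and the chance counts run from under 0.1 to 25 depending on assumed rates and test. That is fair, and the size is given as a range for that reason. But no other AMR analysis appears in the available text, whereas diarrhea gets its own odds-ratio table with confidence intervals. The mismatch with the plan's own definition does not depend on those assumptions.

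**A secondary objective need not be powered.** True, and the bracket in the Sample Size section names diarrhea as the endpoint. What stands is the wording that ties 488 to the objectives as a whole.

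**Any-gene may be a poor main measure.** This stands. A reader might infer that any-gene must be the sole main test because it is the defined endpoint. The documents do not establish that, and steps 5 and 6 show that it can be the weaker choice. What is needed is one participant-level test named in advance.

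**A selected subset could be hard to run.** Also fair. The Study Timeline starts laboratory work in February 2018, when enrollment opens, so a single list of completed pairs cannot be drawn before testing without holding up the laboratory. Under Procedures the treatment code stays closed until the trial ends, so selection within arm is not available either. The rule must work as specimens arrive and without the code.

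**Cross-amplification.** A reader might infer from Study Limitations that one gene will register on several targets. That section says only that primers may pick up related variants lacking their own primer pair, and the amplicons are then sequenced. The inference is not supported.

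**Conclusion.** The concern holds. The plan defines acquisition per participant but lays out only gene-by-gene P-values, in five blocks and without error control. Filled in as drawn, at 244 per arm, the acquisition block could show about 0.5 to 19 chance findings by Fisher's test or 10 to 25 by uncorrected chi-square. This assumes that 500 genes are tested, no true effect, and per-gene acquisition of 0.5% to 20%. The methods and the budget disagree on whether all paired specimens or 250 participants are tested. No AMR power is established.

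Two stronger readings go too far. A reader might infer that 488 is wrong, but it reproduces exactly for diarrhea. A reader might also infer that the AMR comparison is underpowered. The documents give neither an acquisition rate nor an effect, and with an assumed 30% reduction power ranges from 42% to over 99% at 244 per arm. AMR power is unstated, not shown to be low. If only 250 are tested it would be lower, for example 52% instead of 80% at an assumed 40% vs 28%.

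The primary diarrhea analysis is unaffected. This should be corrected before unblinding.

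**What to change.** 1. Add to Table 3 a between-arm comparison of participants with any new gene, with risk difference and 95% CI, and report the number of new genes per participant beside it. Before unblinding, name which of the two is the main AMR test.
2. Apply Benjamini-Hochberg control to the gene-level acquisition block, label gene-level results exploratory, and show the other four blocks without P-values.
3. Reconcile Analytic tests with Table 5. Either test all paired specimens, or, if 250, select by a random rule fixed in advance that uses neither treatment code nor outcomes. One example is random numbers attached to study IDs at enrollment and applied as pairs become complete. Report the resulting number as the AMR analysis set.
4. Reword the Sample Size section so that 488 and 80% power refer to the primary objective only.
5. Optionally, add to Study Limitations that a gene missed in the single pre-travel aliquot would count as acquired.

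**Cost.** Items 1, 2, 4 and 5 are wording and table layout, with no new data. Testing all 1,000 stools adds at least $37,500 at Table 5 unit costs; the personnel lines carry no sample count and are not included. Testing a random 250 adds no laboratory cost but lowers AMR power. Leftover stool and DNA are to be stored, so the rest could be tested later.

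**Downside.** No AMR power can be claimed, and fewer genes will be individually significant. For example, suppose ten of 500 genes truly differ (20% vs 10%), the rest are acquired by 5% in both arms, and there are 244 per arm (all assumed). Unadjusted Fisher tests would flag about 8.5 of the ten plus about 15 others; with Benjamini-Hochberg, about 2.7 of the ten plus about 0.1 others.
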